Objective #4: Each subject will undergo a detailed neuropsychological battery to characterize his or her cognitive and behavioral status—including targeted tests that should be affected by improved verbal retrieval, tests of cognitive functions to which the treatment may generalize, and tests consisting of purportedly unrelated functions to account for global, generalized cognitive improvement. They will also undergo pre-treatment EEG (SORT task with EEG, Semantic Selection task with EEG). These will be used as outcome measures for the treatment trial. The two primary outcome measures will be the COWAT and CVLT. Secondary outcome measures will be SORT and Semantic Selection task, performance and ERP for both sets of tasks.

Objective #5: These subjects will then be enrolled in the active treatment aspect of the study. Enrollment of 80 participants is the target for enrollment in the active phase of the treatment trial. Half the subjects will first receive HD tDCS at 1 mA for 20 minutes over the preSMA region for 10 daily sessions (1 session 5 days per week for a 2 week period). The remaining subjects will initially receive sham HD tDCS; after all follow-up evaluations are completed, they will receive the active HD tDCS treatment.

Objective #6: Each subject will receive follow-up neuropsychological and EEG testing at 1 week, 3 months, and 6 months after treatment. This last time point for evaluation extends from our preliminary work showing that later, further improvement in electromodulation treatments can occur at 6 months post-treatment. HD tDCS active treatment subjects enrolled early in the study will be followed longer than 6 months if agreeable to assess length of effect.

Following completion of this clinical trial, we will be able to determine whether HD tDCS is an effective treatment for the verbal retrieval deficits associated with GWI. An HD tDCS cap is a relatively inexpensive piece of equipment that can be re-used many times for multiple patient treatments. These caps are readily available, and the application of the treatment regimen is straightforward to administer. Thus, this treatment can be utilized in any VA medical center or clinic around the nation. In addition, the neuro-psychological tests and ERP/time frequency findings may function as clinical markers for diagnosis and treatment efficacy in subsequent treatment trials to measure treatment response.

SPECIFIC AIMS

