Hypothesis #2c: An increase in false negative errors and a decreased "Go"P3 ERP response on the Semantic Selection Tasks is indicative of an impaired ability to select a correct memory for retrieval.³³ Conversely, there will be increased false positive errors and a decreased "NoGo" P3 ERP on the Semantic Selection Tasks if a patient cannot inhibit an incorrect memory. *We hypothesize that following HD tDCS therapy, there will be a normalization of the patient's behavior (reduced errors, improved RTs) and/or ERP responses (increased P3 amplitudes for Go and/or NoGo trials) due to modulation of the retrieval circuit, with the changes based on the pre-treatment impaired retrieval function (selection and/or inhibition).*

CLINICAL TRIAL

A. General Experimental Approach.

1. We will screen 120 GWI patients who report subjective word-retrieval deficits over the phone with the COWAT.

2. A subject who on the phone screen has a subjective complaint and decrement in COWAT performance will then be consented and enrolled in person at CBH, and then screened to determine that they have GWI and objective evidence of a verbal retrieval impairment on neuropsychological testing.

3. If a subject scores > 2 SD below the mean on any of the following – the SORT clinical test, COWAT, BNT, and/or CAVLT, the subject will be enrolled in the treatment phase of the study and classified using the CDC criteria for subtype of Gulf War Illness.

4. Subjects will undergo a pre-treatment battery of detailed neuropsychological tests and EEG (SORT and Semantic Selection tasks with ERP). These will be used as outcome measures for the treatment trial.

5. We will enroll 80 subjects in treatment with one-half of the subjects receiving HD tDCS at 1 mA for 20 minutes over the preSMA region for 10 daily sessions; the other half of the subjects will initially receive sham HD tDCS and, after all follow-up evaluations are completed, they will receive active HD tDCS treatment. Participants will be randomly assigned to stimulation and sham conditions via algorithm.

6. Determine at 1 week, 3 months, and 6 months post-last-treatment whether the therapy has been effective by repeating the outcome measures (parallel versions when available) of the SORT, COWAT, BNT, CVLT, and ERP tasks.

B. Subject Recruitment

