Stage 3. Pre-Treatment Testing. Those meeting criteria of having an established GWI and retrieval deficit will be scheduled for a neuropsychological test battery and EEG testing (SORT task with EEG, Semantic Selection task with EEG) as outlined under *Neuropsychological Measures and EEG Tasks* below. The two primary outcome measures will be the COWAT and CVLT. Secondary outcome measures will be SORT task behavioral and ERP measures, as well as Semantic Selection task performance and ERP measures.

Expected sample sizes. Our target sample of 80 Gulf War veterans who will complete the treatment phase of the study will afford us power to detect a statistically significant difference. Treatment-related change in verbal fluency and memory measures will be the primary outcome measures. Treatment-related change in verbal fluency and memory measures will be the primary outcome measures. A study of the effects of single-session tDCS applied to PFC on verbal fluency measures in normal controls showed a large effect-size, with standardized mean difference Cohen's d = 1.18.²⁰ Additionally, this treatment effect estimate on healthy controls is comparable to or exceeds the effect-size estimates for verbal fluency deficits in GWVs with GWI: Letter Fluency averaging over S1-3 Cohen's d = 0.69; S2 Cohen's d = 1.12, S3 Cohen's d = 0.85; Category Fluency averaging over S1-3 Cohen's d = 0.61, S2 Cohen's d = 0.81, S3 Cohen's d = .61.¹¹ For the treatment effect-size for S2, Cohen's $d = 1.18^{20}$, a sample size of 40 per group yields Power=0.92, and for the deficit effect-sizes for S2, Cohen's d = 1.12, and for S3 Cohen's d = .61, Power =0.94 and Power =0.89, respectively.

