The efficacy of HD tDCS will be assessed on each outcome. For the cognitive-behavioral measures (i.e., from SORT, COWA, BNT, CVLT, Trails A & B, Color Word Interference, Digits Forward & Backward, Rey-Osterrieth Complex Figures Test, Grooved Pegboard Test, and Beck Depression Inventory), a mixed-model MANOVA initially will be used to test for omnibus group (active vs sham) effects over time (i.e., Group X Time interaction effects). Given a significant multivariate effect, separate univariate mixed-model ANOVAs for each cognitive-behavioral measure will be evaluated for group (active vs sham) effects over time, and significant interaction effects will be followed up by separate pre- versus post-intervention evaluations for each tDCS group. Verbal fluency has been associated with sex, age, and education^{70, 71 but see 72}; thus, these variables will be included in the models. Additionally, potential mediating effects of IQ (based on NAART) and pre-test to post-test change in executive function, simple attention, working memory, processing speed, and depression (measured via Trails A & B, Color Word Interference, Digits Forward & Backward, Rey-Osterrieth Complex Figures Test, Grooved Pegboard Test, and Beck Depression Inventory) will be explored through covariate mediation modeling. For all testing, data will be thresholded for False Discovery Rates (FDR).

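### Tests of COWAT and CVLT wait on one MANOVA over at least 12 measures at 4 visits, with no estimator, analysis population or missing-data method named; test them directly with a likelihood-based mixed model on all randomised participants

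*Combined protocol and SAP*

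**What the plan says.** The STATISTICAL PLAN lists SORT, COWA, BNT, CVLT, Trails A and B, Color Word Interference, Digits Forward and Backward, the Rey figure, the Grooved Pegboard and the Beck inventory. For all of these together, "a mixed-model MANOVA initially will be used to test for omnibus group (active vs sham) effects over time", meaning the Group by Time interaction. Then: "Given a significant multivariate effect, separate univariate mixed-model ANOVAs for each cognitive-behavioral measure will be evaluated for group (active vs sham) effects over time". Sex, age and education enter the models, and all testing is subject to a false discovery rate threshold.

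Objective #4 and Stage 3 of Subject Recruitment name COWAT and CVLT as the two primary outcomes. The plan makes no exception for them, so they pass through the same gate as the pegboard and the Rey figure.

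On visits, Objective #6 says "Each subject will receive follow-up neuropsychological and EEG testing at 1 week, 3 months, and 6 months after treatment". With the pre-treatment battery that makes four time points.

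On numbers, Objective #5 says "Enrollment of 80 participants is the target for enrollment in the active phase of the treatment trial", and the General Experimental Approach also treats 80 as the number enrolled. The paragraph on expected sample sizes instead says "Our target sample of 80 Gulf War veterans who will complete the treatment phase of the study". Neither allows for loss during the six months of follow-up.

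The documents do not say whether the models are fitted by least squares or likelihood, who is in the analysis, what happens to a participant with a missing score, or how much missing data is expected. The only treatment of missing data is interpolation for EEG electrodes.

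**The concern.** A MANOVA in its usual between-within form works on complete rows. With 12 or more measures at four visits, each row holds at least 48 scores, and one missed subtest at one visit removes the participant from the test that decides whether anything else is tested. A failed gate stops the COWAT and CVLT tests even when those two outcomes are fully recorded.

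Two things are at stake. The first is power: the gate spreads its sensitivity over many secondary measures and loses participants to gaps in any of them. The second is validity: the people left are completers, not everyone randomised. If leaving depends on earlier response, and does so differently in the two arms, the arm difference among completers is not the randomised comparison.

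**Working it through.** **Inputs from the documents.** 80 participants, 40 per arm. Measures, counting Trails A and B and Digits Forward and Backward separately: 12. Visits: 4. Covariates: 3. COWAT test-retest correlation: 0.74 (used in the simulations only).

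**Inputs assumed, because the documents give none.** Missing-data rates, two-sided alpha 0.05, the multivariate effect size, and the dropout patterns.

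**The plan's own power figures.** The sample-size paragraph gives 0.92, 0.94 and 0.89 for d = 1.18, 1.12 and 0.61 with 40 per group. A two-sample t-test at two-sided 0.05 gives 0.999, 0.999 and 0.77, so they do not reproduce. That is a separate matter and does not decide this point. What matters here is that the paragraph quotes power for single standardised differences in fluency and makes no mention of a multivariate gate.

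**Step 1: size of the gate.** Scores per person: 12 × 4 = 48. Group by Time contrasts: 12 × (4 − 1) = 36.

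**Step 2: complete rows left out of 80.**

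Whole follow-up visits missed independently with probability p, baseline complete: 80 × (1 − p)³.
- p = 5%: 80 × 0.857 = 69
- p = 10%: 80 × 0.729 = 58
- p = 15%: 80 × 0.614 = 49

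Under this pattern a single-measure ANOVA loses the same people as the MANOVA.

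Single scores missing independently with probability q: 80 × (1 − q)⁴⁸ for the MANOVA and 80 × (1 − q)⁴ for one measure.
- q = 0.5%: 63 in the MANOVA
- q = 1%: 80 × 0.617 = 49 in the MANOVA; 80 × 0.961 = 77 in a single-measure ANOVA
- q = 2%: 30 in the MANOVA. With 36 contrasts and 5 model terms at least 36 + 5 = 41 complete participants are needed, so the test could not be fitted.

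**Step 3: power of the gate.** For two groups this is a Hotelling-type test. With n complete participants and 3 covariates, error df = n − 5. The F statistic has 36 and n − 40 df and noncentrality (n/4) × D², where D² is the squared Mahalanobis distance between arms. For illustration D² = 1.5, so the noncentrality at n = 80 is 20 × 1.5 = 30.

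| Complete participants | Power, 36 contrasts | Power, 3 contrasts (one measure), same D² |
|---|---|---|
| 80 | 0.59 | 0.997 |
| 69 | 0.44 | 0.992 |
| 58 | 0.28 | 0.976 |
| 49 | 0.16 | 0.944 |

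The last column separates the causes. At the same distance a three-contrast test barely notices the loss of participants. The 36-contrast gate is weak with nobody missing, and its remaining error degrees of freedom shrink quickly as people are lost.

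**Step 4: bias among completers.** Simulations of one outcome at four visits, 40 per arm, correlation 0.74:
- Sham non-improvers leave more often, 24% dropout, true difference 0: completers −0.12 SD, likelihood 0.00. With true difference 0.30: completers 0.19, likelihood 0.31, with the same spread.
- Dropout depends on the last observed change in opposite directions by arm, 10% per visit at 3 and 6 months, true difference 0: completers +0.17 SD with 16.6% false positives; likelihood +0.01 SD with 5.6%.
- Dropout unrelated to response, 10% per visit at 3 and 6 months: both unbiased; power 0.91 for completers and 0.93 for the likelihood model.

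**The case against.** The strongest objection is that the plan never states a deletion rule. The term mixed-model could mean a likelihood fit that keeps incomplete participants. This stands: a reader might infer that the plan restricts the analysis to completers, and the documents do not say so. Complete-row deletion is the conventional consequence of a MANOVA, not a written rule. The reference to 80 completing the treatment phase does not show it either, since it concerns treatment and not follow-up. But the two readings analyse different people, so the plan has to choose. The gate on COWAT and CVLT is explicit under both.

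Three other inferences go too far.
- **That the 48-score rule governs the ANOVAs.** It does not. Each needs only its own measure at four visits and keeps about 77 of 80 at 1% scattered gaps.
- **That a little missing data must remove much of the sample.** That holds for scattered single-score gaps. The tests are given as a battery, so gaps may well cluster by visit, and 5% missed follow-up visits leaves 69.
- **That a likelihood model cures both loss and bias.** It avoids deleting partial records and removes bias under missing-at-random. It does not restore information from people who leave; under random dropout its gain was about two points of power.

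The dropout patterns are also open to challenge. Sham participants are to receive active stimulation after all follow-up evaluations, which gives them a reason to stay, and the direction of bias changed with the pattern chosen. The simulations show that bias is possible; they do not forecast it.

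**Conclusion.** The point holds in this form. Tests of the two primary outcomes depend on a 36-contrast omnibus test that includes secondary measures, and the plan does not say how that test, or the ANOVAs after it, treats incomplete participants.

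On the conventional reading, 69, 58 or 49 of 80 remain if 5, 10 or 15% miss each follow-up visit, and about 49 remain in the MANOVA with 1% scattered gaps. Gate power of 0.59, 0.44 and 0.28 at 80, 69 and 58 rests on an assumed D² of 1.5. Most of that weakness is dimension, and missing data adds to it. Bias among completers is conditional on response-related dropout that differs by arm, and may go either way.

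All missing-data rates and dropout patterns here are assumptions, because the documents supply none. This should be changed before analysis, though the documents do not show that the comparison will be biased.

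**What to change.** In the STATISTICAL PLAN:
- Test COWAT and CVLT directly, not conditional on the MANOVA, with the false discovery rate control applied as already planned.
- Analyse each with a likelihood-based mixed model for repeated measures, using all randomised participants in their assigned arm and every available visit. Include visit as a category, arm by visit, baseline score, sex, age and education. An unstructured covariance is one suitable choice.
- Report the arm difference at 1 week, 3 months and 6 months.
- Use the same model for the other cognitive-behavioral measures.
- State the missing-at-random assumption and add a sensitivity analysis for departures from it.

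The cost is revised wording and a little more analysis work in standard software, with no new data. The downside is reliance on missing-at-random, which the sensitivity analysis is there to probe.

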a) General Cognitive: American National Reading Test (AMNART) for estimated IQ.⁴⁶ This test is chosen to determine if changes from treatment could be associated with IQ and to compare groups that may have differential responses to treatment.

b) Attention and Cognitive Flexibility: Trail Making Test parts A and B⁴⁷; Color Word Interference Test.³⁶

1. For Trails A and B, Trails A measures processing speed and simple attention, and Trails B utilizes the same cognitive components as Trails A with the additional executive function of alternating sequencing. This test is not a direct measure of retrieval but is used to assess for generalization or indirect improvement with HD tDCS. Test-retest reliability is reported as r = 0.745 for Trails A, r = .849 for Trails B, and r = .971 for B-A.⁴⁸

2. Delis-Kaplan Color Word Interference Test³⁶ measures processing speed in the control conditions of color naming and word reading with color word names written in a different ink color than the name measures inhibitory control, an executive function. This test is not a direct measure of retrieval but is used to assess for generalization with HD tDCS, particularly to compare to performance on the inhibitory aspects of the Semantic Selection Tasks. Internal consistency is reported as Cohen's alpha = .62-.86 over age groups from 9 to 89 years of age (Manual), and within in the age GWV, Cohen's alpha = .72-.86. Test-retest reliability is reported as Color Naming r = .76, Word Reading, r = .62, Inhibition r = .75, and Inhibition/Selection r = .65, with lower test-retest reliability coefficients for 50-89 year olds, r = .50-.57.³⁶

3. Digit Span Forwards and Backwards⁴⁹ measures simple attention with digit span forwards and working memory with digit span backwards. This is chosen not because it is to be directly affected by the HD tDCS, but to determine that verbal episodic memory increases are from improvements in attention (digits forward) and to determine if there is generalization to working memory (digits backward). Test-retest reliability coefficients for Digits forwards ranges from .66-.89 and Digits Backwards approximating 0.70.⁵⁰

c) Visual Memory: Rey-Osterrieth Complex Figure Test (Copy and Memory components)⁵¹ The task requires a subject to copy a complex geometric figure and then later to draw what aspects of the figure that they

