still remember. It is included in this study as a check to determine if retrieval improvement is not only in verbal retrieval but also generalizes to nonverbal material retrieval. Reliability across alternate forms is reported as Copy r = .50, Immediate Recall r = .76, and Delayed Recall r = .69, and reliability over one year is Copy r = .18, Immediate Recall r = .47, and Delayed Recall r = .592.⁵²

d) Psychomotor Speed: Grooved Pegboard Test. This test of psychomotor speed utilizes placement of pegs into slots of varying orientations. It is included to assess the specificity of tDCS to retrieval versus generalization to processing speed and the possibility that improved processing speed might mediate improved retrieval. The test has good test-retest reliability (0.91 and 0.85 for right and left hands, respectively).^{53, 54}

e) Beck Depression Inventory.⁵⁵ (Beck et al., 1996) is a subjective questionnaire of depressive symptomatology. The test is not being used as a marker of retrieval, but to determine if mood improvement that may be secondary to HD tDCS application may be accounting for minor improvements in retrieval.⁵⁴ Cronbach's average alpha coefficient average around 0.9, ranging from 0.83to 0.96, test-retest reliability ranges between 0.73 to 0.96.^{56, 57}

2. EEG Tasks

a. Semantic Object Retrieval Test (EEG version).³³ The stimuli in this EEG paradigm comprise 112 pairs of words. There are 56 retrieval and 56 nonretrieval word pairs. The "retrieval" and "non-retrieval" attributes of the word pairs have been validated in previous studies with different groups of subjects. Words will be presented simultaneously one pair at a time for three seconds, with one word above the other. Between trials, a + sign will be presented for three seconds as a visual fixation target. Participants will be instructed to respond "yes" or "no" depending on whether they could think of any particular object upon seeing each word pair. Word stimuli will be presented on an LCD screen placed about 46 inches from the eyes using Stim2 software (Compumedics Neuroscan, USA). Responses will be made by pressing a button under the right index finger for *no*. The entire task lasts about 11 minutes. The retrieval trials index successful access to an object memory represent-ation including verbal information, with the correct nonretrievals indicating a memory search that leads to a conclusion that the features do not combine to activate an object memory.

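### The two primary outcomes, COWAT and CVLT, are tested individually only if a ten-instrument MANOVA is significant, and they then fall under an FDR step with no stated family or level

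*Combined protocol and SAP*

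**What the plan says.** Objective #4 and Stage 3 (Pre-Treatment Testing) both state: "The two primary outcome measures will be the COWAT and CVLT". SORT and Semantic Selection measures are secondary.

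The first paragraph of the Statistical Plan opens with "The efficacy of HD tDCS will be assessed on each outcome". It then says that "a mixed-model MANOVA initially will be used to test for omnibus group (active vs sham) effects over time", and lists ten instruments: SORT, COWAT, BNT, CVLT, Trails A and B, Color Word Interference, Digits Forward and Backward, Rey-Osterrieth, Grooved Pegboard and Beck Depression Inventory. Individual tests follow conditionally: "Given a significant multivariate effect, separate univariate mixed-model ANOVAs for each cognitive-behavioral measure will be evaluated". The paragraph ends by applying FDR thresholds to all testing, with no family, level or procedure for these measures. A 5% FDR appears only in the next paragraph, for the EEG data.

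The protocol itself sets several of these instruments apart from the treatment target:

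- Objective #4 describes part of the battery as "tests consisting of purportedly unrelated functions to account for global, generalized cognitive improvement".
- Digit Span: "This is chosen not because it is to be directly affected by the HD tDCS".
- Grooved Pegboard: "It is included to assess the specificity of tDCS to retrieval versus generalization to processing speed".
- Beck Depression Inventory: "The test is not being used as a marker of retrieval".

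No section exempts COWAT or CVLT from the MANOVA condition or from the FDR step.

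**The concern.** A primary outcome should be tested whatever the other measures show. Here a flat result on tests that the protocol does not expect to move can stop COWAT or CVLT from being tested at all. The more specific the treatment effect, the more null scores dilute the omnibus test. If the MANOVA is significant, an FDR step over the whole battery can again make the threshold for a primary depend on non-primary results. The trial could then end with no valid claim on a primary that would have been significant on its own. The opening promise to assess efficacy on each outcome does not remove the condition stated in the same paragraph.

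**Working it through.** **The plan's own figures.** Stage 3 (Expected sample sizes) gives power of 0.92, 0.94 and 0.89 for d = 1.18, 1.12 and 0.61 with 40 per group. A two-sample t-test at two-sided 0.05 gives 0.999, 0.999 and 0.77, so the stated figures are not reproduced. That is a separate matter and this point does not rest on it. What matters here is that the power statement mentions neither the MANOVA nor FDR.

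**Inputs from the documents.** 40 per arm; ten instruments, or 12 scores when Trails and Digits are each split in two (10 + 1 + 1); COWAT test-retest r = 0.74 (Neuropsychological Measures).

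**Assumptions.** One change score per measure; two-sided 0.05; common between-test correlation 0 to 0.5; no missing data; no effect on tests not named. The plan states no FDR level or family for these measures, so 5% Benjamini-Hochberg over the 12 scores is assumed.

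**Units.** With r = 0.74, the change-score SD is sqrt(2 x (1 - 0.74)) = 0.721 raw SD. An effect of 0.61 raw SD is therefore 0.61/0.721 = 0.846 change-score SD, and 0.61 change-score SD is 0.44 raw SD. The protocol's 0.61 is a deficit size and serves here only as an illustrative magnitude.

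**Omnibus test.** Two-group Hotelling T2 on 12 scores is F(12, 67) with noncentrality (40/2) x D2, where D2 is the squared standardised distance between arms. With one primary at 0.846 and zero correlation, this is 20 x 0.846^2 = 14.3, and the power of the MANOVA is 0.616. COWAT is significant under Holm over the two primaries in 93% of trials.

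**Share of all trials in which COWAT is Holm-significant but the MANOVA is not** (simulation; ranges run over correlation 0 to 0.5):

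| Who responds | 0.846 change SD | 0.61 change SD |
|---|---|---|
| One primary only | 6-32% | 19-38% |
| Both primaries | 0-5% | 4-19% |
| COWAT, SORT and BNT equally, CVLT null | about 0% | 1-6% |
| All four retrieval tests equally | about 0% | at most 2% |

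At d = 1.18 in change-score units, the one-primary figure is at most 7%.

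**Adding FDR.** If COWAT is the only small p-value among 12, Benjamini-Hochberg requires p of at most 0.05/12 = 0.0042. The first Holm step over two primaries requires 0.05/2 = 0.025. Power to declare COWAT at 0.61 change-score SD:

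| Who responds | Direct Holm over two | MANOVA condition plus FDR |
|---|---|---|
| One primary | 67% | about 25-34% |
| Both primaries | 73-74% | about 42-46% |

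In the one-primary case, FDR without the MANOVA condition gives 42-43%. So 67 - 43 = 24 to 67 - 42 = 25 points of the difference come from the battery-wide FDR, and a further 8-17 points from the MANOVA condition.

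**Sensitivity to the MANOVA form.** If the MANOVA takes all three follow-up changes on 12 measures (36 scores), the shares at 0.846 become 19-57% for one primary and 2-19% for both.

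**The case against.** MANOVA followed by univariate tests is a recognised way to handle multiplicity, and the only treatment effect that the protocol cites is d = 1.18, where the loss is small. The Background predicts gains in verbal fluency and word finding, and only potentially in verbal episodic memory. That points to COWAT, SORT and BNT moving together, and the loss is then negligible at 0.846. Using r = 0.74 for every test is also harsh: SORT has r of 0.90 or more, so the same raw effect on SORT is larger in change-score units and makes the MANOVA easier to pass.

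All of this stands as a limit on size. It does not restore an unconditional test of a primary. The 1.18 comes from single-session stimulation of PFC in normal controls, so it does not assure an effect of that size here.

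Three stronger readings are tempting, and the documents do not support them.

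- A reader might infer that the MANOVA step discards about a third of true COWAT effects. That needs one primary to respond with no effect on the other 11 scores.
- A reader might infer that a non-primary effect could deliver a primary claim. COWAT and CVLT must still pass their own tests.
- A reader might infer that the MANOVA is always the weaker test. With 10 scores, both primaries at 0.61 and correlation 0.5, its power is 0.91, against 0.77 for a single t-test.

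**Conclusion.** The structural point holds: both named primaries depend on a ten-instrument omnibus result and then on an FDR step of unstated scope. The loss is material if one primary responds moderately and the rest of the battery stays flat. It is small if both respond at 0.846 change-score SD in the single-contrast form, and close to zero if the retrieval tests respond together at that size or if effects are near 1.18. These magnitudes rest on the stated assumptions and are not bounds, since the plan does not fix the MANOVA form or the FDR family and level. Part of the power that direct testing would recover comes from leaving the battery-wide FDR, not only from removing the MANOVA condition. The case for change is that the improvement is cheap, not that the trial has been shown to fail without it.

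**What to change.** State in the Statistical Plan, before unblinding, that COWAT and CVLT are each tested for active versus sham directly, not conditional on any MANOVA and outside the battery-wide FDR, with family-wise two-sided 0.05 over the two (for example Holm). Name one score for each, since COWAT has letter and category parts. Name one time point or Group x Time contrast for each, since there are follow-ups at 1 week, 3 months and 6 months. Keep the MANOVA condition and FDR for the remaining measures only, and state the FDR family, level and procedure there.

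The cost is wording plus those choices made in advance, with no added participants, visits or tests. The downside is that the primary claim then rests on two tests sharing 0.05 rather than on an omnibus result.
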